If a Veteran is found to be eligible for the study and agrees to participate, the study coordinator will schedule a diagnostic and pre-treatment interview. Potential participants will then meet with a staff-member from the study, who will review study procedures (nature and frequency of assessments, nature of treatments, random assignment to treatments), answer any questions, and obtain written informed consent. During the COVID-19 pandemic, this interaction will take place over telehealth. Primary care providers will follow routine treatment and referral procedures regardless of patient interest in the study.

We expect similar enrollment and recruitment rates at the Portland and VA Puget Sound. There is evidence that a substantial pool of potential participants exists, suggesting that the goal of recruiting 192 participants over the course of the study is feasible. Even allowing for more rigorous diagnostic procedures, exclusionary criteria, and a moderate refusal rate, the sample size should be easily attained. Total enrollment for the study at both sites would be 96 participants per site (48 CABA and 48 TAU), for a total of 192 participants (96 CABA and 96 TAU).

Steps to minimize dropout rate: We had a relatively low non-completer rate 11% among subjects enrolled in [CABA, Version 14, 8.12.2020] VA Central IRB Protocol Template – version 10/26/2012

our funded CCT study with OEF/OIF Veterans with mTBI. We partially attribute the low non-completer rate to reminder phone calls and financial incentive. Since compensation and reminder phone calls will once again be used in the proposed study, we expect a low attrition rate. Subjects will be compensated for time involved in the study as described below. We will also call all subjects to remind them of each session and study visit.

**Reimbursement for time and travel:** Compensating subjects for their participation reduces attrition rates. We plan to compensate participants at each assessment point. They will receive a payment of \$50 after each of the first three assessments. For completion of all three assessments, total compensation will be \$150.

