Power calculations can be made for repeated measures designs under specified assumptions. Hedeker et al. extend Diggle et al.'s method for various covariance structures. Procedures described by Hedeker et al. for Random Regression Models were used for the proposed study to estimate needed sample size using RMASS (see Hedeker <http://tigger.uic.edu/~hedeker/ml.html>). Data from our previous studies were used to calculate effect sizes. The design consists of a 2 (sites) X 2 (CABA vs TAU) X 4 (baseline, 7, and 14 weeks) where the slope is the dependent measure. Site and Treatment by Site interaction were included as "nuisance parameters", that is, included to account for possible overall site effects (Site) or possible site differences in treatment effects (Treatments X Site). With a balanced design (equal numbers at each site in each group), ignoring these would not increase the probability of Type I error, but would increase the Error Sum of Squares (SS) and probability of Type II error. The main effect of treatment represents the common effect size across sites if there is one, or the average site effect, if there is heterogeneity across sites. This is true because sample sizes will be balanced across treatment groups and sites. In any case, the analysis procedures will include site and site interaction effects to avoid allowing site effects to bias treatment comparisons. However, if we detect imbalances between the treatment groups within each site, we will follow the primary analyses with subsequent analyses considering the imbalances to verify that conclusions are not affected by imbalances.

Other assumptions needed are number of repeated measures, alpha-level, nature of the hypothesis (one- or two-sided), drop-out rate, and variance-covariance matrix of the longitudinal data. We assume an overall Type-I error levels alpha of .01 to .02, drop-out rate of 15%, and autoregressive covariance structure, with correlation between sequential assessments set at 0.45. Autoregressive covariance structures assume points closer together in time are more correlated than points further in time, which is more plausible compared to the equal correlation between all pair of assessments regardless of time separation assumed by the compound symmetry design. *When multiple analyses are conducted for a given hypothesis, Type I error rates will be controlled*

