*by a Westfall-Young procedure, we would include an alpha level of .04 for Hypothesis 1a, .03 for Hypothesis 1b and 2a, and .05 for Hypothesis 2b.* We estimate that with the proposed sample size of 192 (15% drop-out) patients (96 for each of the two groups), the study will have minimum power of 80% to yield a statistically significant result for a medium effect size. Hedker et al. defined medium effect size in this model as a between-group difference increasing linearly from 0 at baseline to .5 SD units at the last time point. Hypothesis 2b is a cross-sectional hypothesis using data collected only in the week 14 of the study. The proposed sample size will provided us with a minimum power of 90% to detect a medium to large effect size. The former and foundational Behavioral Activation for PTSD study by [name] and [name] yielded the following rates which also informed our proposed sample size determination: 192 screened, 81 enrolled, 10 dropped (12.3% dropout rate), 101 screen failures.

**Outcome analyses:** Data analyses will proceed in stages. Descriptive statistics and exploratory graphing such as frequencies, means, standard deviations, stem and leaf diagrams, and scatterplots will be used to assess normality of data in terms of presence of skew and/or outliers. Continuous outcome data will be transformed if necessary using an appropriate transformation such as the log transform for skewed long tailed data. Prior experience with this kind of data leads us to expect that for all variables, the distributions will be skewed and the variances not homogeneous. Similarly, potential covariates will be summarized with descriptive statistics and graphs to determine the most appropriate way to treat these variables (e.g., continuous, categorical, or interval representation). For outcome measures acquired at baseline, 7, and 14 weeks, the analytical approach will address the nature of the outcome, as well as accommodate the within

individual variability due to the repeated assessments. Results from will be inspected for bias due to drop-outs or missing data.

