**Hypothesis 1a)** PTSD symptom severity. Dependent variables: CAPS-V and PCL-5.

**Hypothesis 1b)** Functional impairment. Dependent variables: HVLTR, WAIS-IV (Digit Span subtest), DKEFS (Trails subtest), and COWAT (Verbal Fluency).

Independent variables: Treatment group (2 levels, CABA and TAU), & Time (3 levels, Weeks 0, 7, and 14). Statistical Analysis: We will analyze data on all randomized subjects in whom we have a baseline assessment and at least one post-baseline evaluation by Mixed effects model methods. Preliminary inspection of data will determine whether the outcome is nearly normal, or whether an appropriate transformation is required, or whether a generalized linear mixed model should be considered. The mixed effects model method provides an estimate of the individual variability around the population trend, the variability of the individual intercepts (baseline values) and slopes (changes across time), and the correlation between them. A fully saturated treatment by time model will be utilized for inference. Covariance structure will be chosen based on Akaike's Information Criterion (AIC). Random group level treatment effects will also be evaluated for importance based on the model AIC. This allows for any group level effects to be incorporated into the model. Denominator degrees of freedom will be calculated using the Kenward-Roger small sample correction. The design is a 2 (sites) X 2 (CABA vs TAU) X 3 (baseline, 7, and 14 weeks). The interaction of Site and Treatment X Site will be included and tested as

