"nuisance parameters". However, we do not anticipate any Treatment by Site or Site effects with the balanced design (equal numbers at each site in each group), our standard training procedure of both sites and standard operating procedure used by both sites. In any case, the analysis procedures will include site and site interaction effects to avoid allowing site effects to bias treatment comparisons. If we detect any imbalances between the treatment groups within each site, we will follow the primary analyses above with subsequent analyses considering the imbalances to verify that the conclusions are not affected by imbalances. Analyses will be conducted within and across nested levels of the study design; this will involve within-subject analyses (comparison of occasions of measurement nested within an individual), as well as between-subject analyses (comparison of the CABA and TAU groups, comparison of groups within a site, comparison of sites, etc). Any treatment group comparison can be adjusted for subject-specific characteristics and adjustments for changes in these characteristics over the course of the study can be incorporated into single-subject analyses. All comparisons described in this section can be effectively analyzed using PROC MIXED in SAS statistical software. Based on our ongoing studies, we expect a drop-out rate of <15% after baseline assessment but prior to first post-baseline evaluation. The drop-out rate is taken into account in power analyses, see above.

**Hypothesis 2a)** Patient-centered outcomes. Dependent variables: BDI-II, NSI, and SLS. Independent variables: Treatment group (2 levels, CABA and TAU), and Time (3 levels, Weeks 0,7,14). Statistical Analysis: Data will be analyzed similar to hypotheses 1a and 1b.

**Hypothesis 2b)** Treatment satisfaction. Dependent variables: CSQ. Independent variables: Treatment group (2 levels, CABA and TAU). Statistical Analysis: Hypothesis 2b will be tested using Analysis of Variance, comparing the two groups on the treatment credibility and satisfaction (CSQ).

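### The site terms for 1a, 1b and 2a are not said to vary over time, so read literally the Treatment x Site test is diluted by baseline; the 2b ANOVA leaves site out

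*Combined protocol and SAP*

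**What the plan says.** The site terms first appear in section 5.6, Sample size and power. The dependent measure there is the slope, and Treatment x Site is given the job of capturing site differences in the treatment effect. The same paragraph says that ignoring site in a balanced design would not raise Type I error, "but would increase the Error Sum of Squares (SS) and probability of Type II error".

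The analysis text for 1a and 1b models the repeated scores, saturated in treatment by time. On site it says: "The interaction of Site and Treatment X Site will be included and tested as" nuisance parameters. Neither Site x Time nor Site x Treatment x Time is named. The sentence just before gives the design as 2 sites by 2 arms by 3 times, and the text that follows promises site and its interactions without listing them. Hypothesis 2a is to be analysed in the same way.

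For 2b the only independent variable listed is treatment group: "Hypothesis 2b will be tested using Analysis of Variance, comparing the two groups".

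**The concern.** On the slope scale, Treatment x Site is a site difference in change. In a model of the scores themselves, a term of that name without time shifts all visits equally, including baseline, where randomisation means there is no treatment effect to differ. So the term to be tested would not measure what the power paragraph assigns to it, and a programmer could defensibly fit either of two models. The question is a live one: the Control Intervention paragraph says usual care varies between the sites, although it also describes steps to standardise it. At stake are the sensitivity of the site test and, for 2b, a little precision that the plan's own reasoning says should be kept.

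**Working it through.** **The plan's own figures.** No power is claimed for any site term. The 2b claim (at least 90% for a medium to large effect) can be checked: 96 x .85 = 81.6 per arm, z = .5 x sqrt(81.6/2) = 3.19, power = Phi(3.19 - 1.96) = 89% at 0.5 SD. At 0.6 SD, z = 3.83 and power is 97%. That agrees. The 80% claim for 1a, 1b and 2a concerns the treatment effect and is not at issue here.

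**Inputs.**
- Allocation: "96 participants per site (48 CABA and 48 TAU" (section 5.2).
- Dropout: "we expect a drop-out rate of <15% after baseline assessment but prior to first post-baseline evaluation". At 15%, 48 x .85 = 40.8, about 41 per cell.
- Correlation: .45 between sequential assessments, autoregressive. For an outcome measured only at weeks 0 and 14 this is .45 if those two visits count as sequential, or .45^2 = .2025 if .45 is per 7-week step. Both are shown.
- Visits (Table 3): CAPS-V and the neuropsychological battery at weeks 0 and 14; PCL-5, NSI, BDI-II and SLS at weeks 0, 7 and 14; CSQ at week 14.
- Alpha: the power text has "We assume an overall Type-I error levels alpha of .01 to .02" and then "we would include an alpha level of .04 for Hypothesis 1a, .03 for Hypothesis 1b and 2a, and .05 for Hypothesis 2b". Sidedness is listed as an assumption but not stated. I use two-sided .05 and give a range below.
- Site difference in effect, D: not in the documents. Assumed 0.5 SD at week 14 (0.5 SD at one site, 0 at the other), rising linearly from 0.

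**Two visits, 41 completers per cell, SD = 1.**
- Three-way term: effect .5, SE = sqrt(4 x 2(1 - rho)/41).
- Constant term: it averages the visits, so effect = (0 + .5)/2 = .25, SE = sqrt(4 x (1 + rho)/2/41).
- rho = .45: three-way SE .328, z = 1.53; constant SE .266, z = .94.
- rho = .2025: three-way SE .394, z = 1.27; constant SE .242, z = 1.03.

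**Three visits, AR(1) .45.**
- The constant term weights the visits 1, .55, 1 (sum 2.55). Effect = (.55 x .25 + 1 x .5)/2.55 = .25; SE = sqrt(4 x (1.45/2.55)/41) = .236; z = 1.06.
- The week-14 three-way contrast has the SE above for rho = .2025, z = 1.27.

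The last two columns repeat this by generalised least squares with 48 per cell, keeping the baseline scores of the 15% lost before week 7.

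| Outcome | Constant, completers | Three-way, completers | Constant, GLS | Three-way, GLS |
|---|---|---|---|---|
| Two visits, rho .45 | 15.6% | 33.3% | 14.3% | 34.3% |
| Two visits, rho .2025 | 17.8% | 24.5% | 16.5% | 25.6% |
| Three visits | 18.6% | 24.5% | 17.2% | 25.6% |

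**Sensitivity (GLS).**
- D = 1.0 SD, three visits: 52% v 74%.
- Site difference already complete by week 7, D = 0.5: 23% v 26%.
- Alpha .02 to .04, D of 0.5 to 1.0 SD: constant-to-three-way power ratio .61–.68 for three visits, .34–.45 for two visits at rho .45.
- Three visits, three-way interaction tested on 2 df instead of as the week-14 contrast, D = 0.5: 20%.

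**Treatment effect.** With 48 per cell and the covariance taken as known, the SE of the week-14 treatment effect is the same with or without time-varying site terms: 0.1917 for three visits, 0.1608 for two visits at rho .45.

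**2b without site.** A site difference of delta SD in mean CSQ inflates the variance by 1 + delta^2/4 in balanced arms. At d = 0.5:

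| delta (assumed) | Inflation | Power |
|---|---|---|
| 0 | 1.000 | 89.1% |
| 0.2 | 1.010 | 88.8% |
| 0.3 | 1.0225 | 88.5% |
| 0.5 | 1.0625 | 87.3% |

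**The case against.** The strongest reply is that the sentence is loose wording. The power paragraph puts the term on the slope, where it already is the three-way interaction. The design line crosses site, arm and time, and the text promises site interactions in general. The site terms are nuisance terms, no power is claimed for them, and no site effects are expected given common training and procedures. Even the better test reaches only about a quarter to a third power for 0.5 SD, so the trial could not settle site heterogeneity either way.

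Most of this stands, and it is why the point is ambiguity and not error. It does not remove the need to say which terms are fitted, since the plan undertakes to test them.

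A reader might infer three stronger things that the documents do not support:
- That power for the site test is halved in general. That needs a two-visit outcome and a week 0–14 correlation of .45. For three-visit outcomes with dropout at alpha .05 the ratio is about two thirds to four fifths, and the terms nearly coincide if the difference is complete by week 7.
- That the treatment comparison is biased or clearly less precise. With arms balanced within site as planned, it is unbiased. Because the SE comparison above takes the covariance as known, it cannot show site variance entering the residual. That inflation would be 1 + (delta^2/4)/1.10 for a two-visit change at rho .45, or 2% to 6% for delta of 0.3 to 0.5 SD, but no such site difference is given.
- That a full factorial would cost precision by averaging sites without weights. At the planned equal site sizes the cost is zero, and the plan openly says the main effect is an average over sites.

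**Conclusion.** The concern holds as a minor point of specification. The analysis text does not name the time-varying site terms. The literal reading gives a test that does not match the change-over-time effect and has less power when the site difference grows to week 14: at D = 0.5 SD, roughly 14–18% against 24–34% for two-visit outcomes, depending on the correlation, and about 17% against 26% for three-visit outcomes. The 2b model departs from the plan's own argument for keeping site, at a cost of 0 to 2 power points.

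These sizes rest on assumed site differences, two-sided alpha .05, 15% early dropout and the plan's correlation of .45. They do not affect the validity of the treatment comparison in the balanced design.

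**What to change.** In the 1a/1b analysis text, which also governs 2a, state that the model includes Site and Site x Time, and that site heterogeneity of the treatment effect is tested by Site x Treatment x Time. Whether that test sits in the same model or a separate one is the sponsor's choice. For three-visit outcomes, say whether it is the week-14 contrast or the 2-df test. Describe the result as low-powered. In the 2b text, add site as a factor in the ANOVA.

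This is a wording change with no new data. Site x Time uses one degree of freedom for two-visit outcomes and two for three-visit outcomes, and site uses one in 2b.

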**Exploratory Investigation to Provide Guidance for Future Research Directions:**

Guidance for future research will be obtained through exploratory analyses including possible mediator and moderator variables in addition to secondary outcome variables, including measures of neuropsychological test performance and general functioning. We will also investigate whether CABA-associated treatment gains are maintained over a 6 month follow-up period. The effect of moderator and mediator variables will be explored following the procedures recommended by Kraemer, Cohen and Cohen and Busemeyer and Jones.

**Anticipated time table:** Table 4 depicts a four-year study plan with 6 months for start-up and 6 months termination; 156 weeks for enrollment and 6 month follow up assessments. The study will be fully enrolled within 39 months of the start of funding of the trial. The last group of subjects will exit by month 42.

**Table 4. Anticipated Time Table**

	Year One				Year Two				Year Three				Year Four			
	Q1	Q2	Q3	Q4	Q1	Q2	Q3	Q4	Q1	Q2	Q3	Q4	Q1	Q2	Q3	Q4

Start-Up Phase: Establish infrastructure; staff hiring & training; IRB approval; complete manual; fidelity monitoring implementation; & set up data management systems.																	
Data Acquisition: CABA: assessments + CABA; TAU: assessments; Tx fidelity																	
Analysis and Dissemination: Data analysis; manuscript; manual dissemination																	

**Dissemination plan:** We will present preliminary and final results at relevant national conferences. Our co- investigators are well-versed in conducting large-scale cyber-seminars for VA and DoD audiences. Drs.

[name] and [name] have worked with the VA’s Center for Information Dissemination and Education Resources and Quality Enhancement Research Initiative to conduct multiple cyber-seminars for large, national audiences of over 500 participants at low- to no-cost, and plan do conduct such seminars on the findings from this trial. Multiple VA and DoD research reports and academic articles are planned for dissemination of findings. A website will be established and the treatment manual will be made available online. This trial would provide critical data on feasibility of providing PTSD treatment to Veterans with mTBI, which is a key issue for the VA and DoD. We expect to disseminate findings in multiple research reports throughout the course of the trial as well as at least 4 peer reviewed academic journal articles following trial completion.

### 5.7 Withdrawal of Subjects

Should any findings arise during assessment study visits which might affect the participant’s health or welfare, the study team will address those findings directly with participants during the assessment study visit within which the issues are discovered. The study team will use CPRS to identify the participant’s health care providers as well as communicate the findings with those providers and follow-up via telephone as needed.

The co-PIs will recommend termination of participation, provide appropriate referrals, and engage in follow-up if substantial decline in functioning is observed at any assessment study visit for all participants and/or treatment visits for those assigned to the CABA treatment intervention. Participation in this study therefore, will be terminated at the discretion of study personnel (with final determination by co-PI’s), based upon clinical observations and judgments regarding the safety of continued participation to the patient’s physical and/or psychological health and well-being. Additionally, if participants fail to comply with important instructions that are part of the approved study protocol, such as actively abusing substances, participation will be terminated without consent.

Although the proposed study poses no serious risks to participants, participants may notify research personnel about pre-existing mental health issues that have not been previously identified by other VA providers. Therefore, participants will be referred to the VA’s Mental Health Division for further

assessment and/or treatment if a previously undiagnosed psychiatric disorder is identified. We will inform participants of this procedure as part of the informed consent process and participants must agree to this procedure to be eligible to participate in the study. This ensures that we can adequately manage any pre-existing clinical issues that become apparent through subject evaluation.

If a participant chooses to withdraw from the study, study personnel or Drs. [name] or [name] will refer the patient back to their providers in Primary Care for further assessment of treatment needs. The reason for withdraw will be documented. Participants who choose to withdraw early will still be allowed to continue participation in follow-up assessments and would continue to receive financial reimbursement for doing so, but this would be completely voluntary. A possible consequence of a participant choosing to withdraw early from the study is that he/she will likely continue to experience cognitive and/or PTSD symptoms. Without treatment, these symptoms may worsen over time.

